4.2 PRIMARY, SECONDARY AND EXPLORATORY EFFICACY ANALYSIS

The primary efficacy analysis evaluates the mean change from baseline to 12 weeks of treatment as measured by the Vineland-3 ABC three-domain GSV composite. The difference in the mean change from baseline between each of the two active doses and placebo will be extracted as contrasts from the ANCOVA model.

The efficacy analyses of the secondary endpoints and of the CRRI total score evaluate the mean change from baseline to 12 weeks of treatment. The difference in the mean change from baseline of the two active doses and placebo will be extracted as contrasts from the ANCOVA model.

The efficacy analysis of CGI-I evaluates the overall score at 12 weeks of treatment. The difference of the two active doses and placebo will be extracted as contrasts from the ANCOVA model.

4.2.1 Definition of Primary Endpoint

The primary endpoint is Change from baseline to Week 12 in the Adaptive Behavior Composite score of the Vineland[™] Adaptive Behavior Scales, Third Edition (Vineland[™]-3), as defined in Section 1.1 of SAP (see Table 1).

4.2.2 Main Analytical Approach for Primary, Secondary, CRRI and CGI-I Endpoints

The analyses of primary, secondary, CRRI and CGI-I efficacy endpoints will include all participants in the Efficacy Analysis Population.

An analysis of covariance (ANCOVA) model will be used to compare treatment effects for the primary, secondary, CRRI and CGI-I efficacy endpoints across the overall Efficacy Analysis Population of adolescents and adults. The model will include treatment as main effect, individual age at screening, IQ, and baseline score as covariates. Treatment differences will be estimated together with their 80% confidence intervals as derived from the model and their associated p-values.

The ANCOVA model will be applied to change from baseline data y_{ij} of participants i, and treatment $j \in \{\text{placebo (reference)}, \text{low dose}, \text{high dose}\}\)$ as follows:

$$y_{ij}=\mu+t_i+a_i+IQ_i+BL_i+\epsilon_{ij}$$

where μ gives the overall endpoint mean change, followed by the fixed effect t which models the effect of treatment, age a, IQ, the endpoint baseline value BL, and ϵ , which gives the overall error term with $N(0, \sigma_{\epsilon}^2)$.

Table 8 Efficacy Statistical Analysis Methods

Endpoint	Statistical Analysis Methods
Primary	ANCOVA
Secondary	
CRRI, CGI-I	

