8.1.5.1 Vineland Adaptive Behavior Scale, Third Edition (Vineland™-3)

The Vineland[™] is an instrument that measures communication, daily living skills, socialization, motor skills (only used in children up to 9 years of age) and maladaptive (not assessed in this study) behaviors of individuals with developmental disabilities (Sparrow et al 2005). The Comprehensive Interview will be administered to a participant's support person in this study, during which the rater or clinician will ask to the support person open-ended questions relating to the participant's activities and behavior. Domain scores will be obtained for the individual domains of Socialization, Communication, and Daily Living Skills and used to calculate the Vineland[™] Adaptive Behavior Composite score. Standardized scores on the Adaptive Behavior Composite score range from 20 to 160, with higher scores indicating better adaptive functioning.

VinelandTM-3 will be administered at different visits (see SoA in Section 1.3) by central raters via live, secure telemedicine platform. For any individual participant, the same rater should administer the VinelandTM.

This interview will take approximately 45 to 60 minutes. The rater will interview the support person to complete the VinelandTM.

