1. INTRODUCTION

The objectives of this Phase 2 proof-of-concept study (BP41316) is to investigate the efficacy, safety, and tolerability of Alogabat in adolescents and adults (15 to 45 years of age) with autism spectrum disorder (ASD), with a target on the core symptoms of ASD of social communication deficits, and restricted and repetitive behaviors (RRBs) and interests. In addition, a set of biomarkers linked to the mechanism of action of the study drug or to ASD-related alterations is investigated in a representative patient population to pilot the identification of responder subgroups. To date, very few studies have investigated the effect of pharmacological treatments on the core symptoms of ASD and consequently no pharmacological agents are approved that offer a treatment for the core symptoms in this population of high unmet clinical need.

A key challenge in the development of new therapies to treat the core symptoms in ASD is the change of symptoms across different stages of development in longitudinal studies in both social communication deficits as well as in RRBs (Simonoff et al. 2020; Richler et al. 2010; Pender et al. 2020). The presentation of RRBs is known to be associated with age and the level of intellectual functioning (Lam and Aman 2007, Esbensen et al 2009, Richler et al 2010, Kim and Lord 2010, Uljarevic et al 2022). Thus, interventions may have different effects, depending on age and intelligence quotient (IQ), on individuals with ASD and treatment effects in older adolescents and adults may not be extrapolated to effects in the pediatric population, given the potential difference in manifestations, both quantitatively and qualitatively, of social communication deficits and RRBs with age.

Adolescents and adults aged 15 to 45 years with ASD are enrolled in this study to allow for the generation of data on the safety and tolerability, and the potential efficacy in these age groups.

Analyses of the primary and secondary endpoints as described in the protocol will be performed as planned.

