1.1 OBJECTIVES AND ENDPOINTS

Table 1 Primary and Secondary Objectives

Primary Objective	Endpoint
To evaluate the efficacy of 12-week treatment with alogabat compared with placebo in treating social communication deficits in participants with Autism Spectrum Disorder (ASD)	 Change from baseline to Week 12 in the Adaptive Behavior Composite score of the Vineland[™] Adaptive Behavior Scales, Third Edition (Vineland[™]-3)
Secondary Objectives	Endpoints
To evaluate the safety and tolerability of a 12-week treatment with alogabat in 15-to 45-year-old participants with ASD	 Incidence and severity of adverse events (AEs) and serious adverse events (SAEs)

	Incidence of treatment discontinuations due to AEs Change from baseline over time and
	 Change from baseline over time and incidence of clinically relevant abnormalities in vital signs including orthostatic changes, electrocardiogram (ECG) parameters and safety laboratory values including the incidence of marked laboratory abnormalities
	 Change from baseline over time in suicide risk (using the Columbia-Suicide-Severity Rating Scale [C-SSRS])
	 Incidence of daytime sleepiness assessed with the Karolinska Sleepiness Scale (KSS), the Epworth Sleepiness Scale (ESS) or the ESS for children and adolescents (ESS- CHAD), and the Sudden Onset of Sleep Questionnaire
To evaluate the efficacy of a 12-week treatment with alogabat compared with placebo on restricted and repetitive behaviors (RRBs)	Change from baseline to Week 12 in behavior/symptoms as measured by all domains of the Repetitive Behavior Scale-Revised (RBS-R) scale
To evaluate the efficacy of a 12-week treatment with alogabat compared with placebo on social behaviors	Change from baseline to Week 12 on the Vineland-3 Socialization domain
To evaluate the efficacy of a 12-week treatment with alogabat compared with placebo on communication skills	Change from baseline to Week 12 on the Vineland-3 Communication domain

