2.2 SAMPLE SIZE DETERMINATION

Approximately 105 participants with ASD randomized in a 1:1:1 ratio between two active dosing regimens and placebo need to be recruited in order to obtain evaluable data from approximately 84 participants after 12 weeks of treatment. Evaluable data from 84 ASD participants provides at least 80% power to detect a mean difference between baseline and 12-week follow-up of 4.5 points on a Vineland $^{\text{TM}}$ -3 composite between any active treatment arm and the placebo arm with α = 0.10 error control (1-sided). The minimally detectable difference in this cohort is 2.7 points. It is assumed that the standard deviation of the differences between baseline and 12 weeks follow up is 8.0 points, that 20% of participants will not provide evaluable data, and that the participants recruited will consist of at most 25% low-functioning participants, at most 25% female participants. Because the purpose of this study is exploratory, no adjustment for comparison of multiple active doses to a single placebo arm is performed.

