The Groton Maze Learning Test (GMLT) measures executive function using a maze learning paradigm. A 10 x 10 grid of tiles is presented to the participant on the screen. A 28-step pathway is hidden among these tiles. A blue tile indicates the start and a tile with red circles indicates the finish. The participant must move one step at a time from the start toward the end by touching a tile next to their current location. If the correct move is made a green checkmark appears and if the move is incorrect a red cross is revealed. Once completed, they are returned to the start location to repeat the test and must try to remember the pathway they have just completed. The software records the total number of errors made in attempting to learn the same hidden pathway on 5 consecutive trials during a single session. This assessment takes approximately 7 minutes to perform.

 Table 7
 Efficacy Endpoints Details and Description

Efficacy Endpoint	Description
Vineland-3 ABC Composite GSV	A raw score will be calculated for each subdomain of the Socialization (interpersonal relationships, play and leisure time, coping skills), Communication (receptive, expressive, written) and Daily Living Skills (personal, domestic, community) domain as the sum of the scores for each item within the subdomain.
	The raw scores for each of the 9 subdomains will be mapped to GSV scores. A conversion table for mapping raw scores to GSV scores is found in Appendix 3. This was based on Table B.2 in the Vineland-3 manual.
	The Vineland-3 ABC Composite GSV score will be calculated as the mean GSV score (i.e. summing the 9 GSV subdomain scores and dividing by 9).
Vineland-3 Socialization GSV	A raw score will be calculated for each subdomain of the Socialization domain (interpersonal relationships, play and leisure time, coping skills) as the sum of the scores for each item within the subdomain.
	The raw scores for each of the 3 subdomains will be mapped to GSV scores.
	The Vineland-3 Socialization GSV score will be calculated as the mean GSV score (i.e. summing the 3 GSV subdomain scores and dividing by 3).

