t_vabs3_ancov a	Efficacy	Vineland-3 SOC GSV Score ANCOVA age interaction
t_vabs3_ancov a	Efficacy	Vineland-3 SOC GSV Score ANCOVA IQ interaction
t_vabs3_ancov a	Efficacy	Vineland-3 COM GSV Score ANCOVA no interactions
t_vabs3_ancov a	Efficacy	Vineland-3 COM GSV Score ANCOVA age interaction
t_vabs3_ancov a	Efficacy	Vineland-3 COM GSV Score ANCOVA IQ interaction
t_vabs_cfb	Efficacy	Vineland-3 ABC GSV Score Change from Baseline
t_vabs_cfb	Efficacy	Vineland-3 SOC GSV Score Change from Baseline
t_vabs_cfb	Efficacy	Vineland-3 COM GSV Score Change from Baseline
t_vabs_cfb	Efficacy	Vineland-3 DLS GSV Score Change from Baseline
t_vabs_cfb	Efficacy	Vineland-3 ABC Standard Score Change from Baseline
t_vabs_cfb	Efficacy	Vineland-3 SOC Standard Score Change from Baseline
t_vabs_cfb	Efficacy	Vineland-3 COM Standard Score Change from Baseline
t_vabs_cfb	Efficacy	Vineland-3 DLS Standard Score Change from Baseline
t_rbsr_ancova	Efficacy	RBS-R Total Score ANCOVA no interactions
t_rbsr_ancova	Efficacy	RBS-R Total Score ANCOVA age interaction
t_rbsr_ancova	Efficacy	RBS-R Total Score ANCOVA IQ interaction
t_rbsr_cfb	Efficacy	RBS-R Total Score Change from Baseline
t_rbsr_cfb	Efficacy	RBS-R Subscale Score (3FM) Change from Baseline

[figure not shown]
t_crri_ancova	Efficacy	CRRI Total Score ANCOVA no interactions	
t_crri_ancova	Efficacy	CRRI Total Score ANCOVA age interaction	
t_crri_ancova	Efficacy	CRRI Total Score ANCOVA IQ interaction	
t_crri_cfb	Efficacy	CRRI Total Score Change from Baseline	
t_crri_cfb	Efficacy	CRRI Subscale Score (5FM) Change from Baseline	
t_cgii_ancova	Efficacy	CGI-I Overall Score ANCOVA no interactions	
t_cgii_ancova	Efficacy	CGI-I Overall Score ANCOVA age interaction	
t_cgii_ancova	Efficacy	CGI-I Overall Score ANCOVA IQ interaction	
t_cgii_mmrm	Efficacy	CGI-I Overall Score MMRM	
t_cgii	Efficacy	CGI-I Overall Score	
t_cgii_cat	Efficacy	CGI-I Proportions per Rating Category	
t_cgis	Efficacy	CGI-S Overall Score	
t_cgis_cat	Efficacy	CGI-S Proportions per Rating Category	
t_bai_cfb	Efficacy	BAI Total Score Change from Baseline	
t_pras_cfb	Efficacy	PRAS-ASD Total Score Change from Baseline	
t_ssp_cfb	Efficacy	SSP-2 Summary Score Change from Baseline	
t_aasp_cfb	Efficacy	AASP Quadrant Summary Score Change from Baseline	
t_promis_cfb	Efficacy	PROMIS Sleep-Disturbance T-Score Change from Baseline	
t_promis_cfb	Efficacy	PROMIS Sleep Related Impairment T-Score Change from Baseline	
t_<>	Efficacy	Change from Baseline in EEG beta power	

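### The declared Vineland-3 composite has no model-based treatment comparison on its standardized scale: every planned Vineland ANCOVA uses Growth Scale Value means, a metric absent from the protocol

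*SAP*

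**What the plan says.** **Declared endpoint.** SAP Table 1 gives the primary endpoint as "Change from baseline to Week 12 in the Adaptive Behavior Composite score of the Vineland" scales, third edition. Protocol Table 6 and SAP 4.2.1 say the same. Protocol 8.1.5.1 derives the composite from the Socialization, Communication and Daily Living Skills domain scores and states: "Standardized scores on the Adaptive Behavior Composite score range from 20 to 160". The protocol does not mention GSVs.

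**Analysed variable.** SAP 4.2 evaluates the change "as measured by the Vineland-3 ABC three-domain GSV composite". SAP Table 7 computes that composite by "summing the 9 GSV subdomain scores and dividing by 9". The Socialization and Communication GSV scores are each a mean of three subdomain GSVs.

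**Two scores, not one.** SAP 4.1.3 describes standard scores as relative to an age norm and a GSV as a measure of the person's own ability, used to track progress. Table 7 has separate rows for the ABC GSV composite and the ABC standard score.

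**Outputs.** SAP Appendix 1 lists Vineland ANCOVA tables for ABC, Socialization and Communication, all on GSV. The ABC forest plots are also on GSV. The standard scores appear only in tables such as "Vineland-3 ABC Standard Score Change from Baseline", which belong to the descriptive analyses of SAP 4.3.

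**Continuity and benchmarks.** SAP 1 states: "Analyses of the primary and secondary endpoints as described in the protocol will be performed as planned". SAP 2.2 repeats from Protocol 9.2 the 4.5-point target, the SD of 8.0 and the sentence "The minimally detectable difference in this cohort is 2.7 points", without saying which Vineland scale the points belong to.

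**The concern.** An age-normed score and an individual ability score can move differently over 12 weeks and can give different p-values. On the scale the protocol describes, the primary endpoint and the two Vineland secondary endpoints would have no adjusted active-versus-placebo difference, interval or p-value. SAP 2.1 bases its gating criteria on ANCOVA p-values, so the Vineland evidence feeding that decision would come from a score the protocol does not define.

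A reader of the SAP would not learn this from its introduction or its endpoint definition, both of which indicate that nothing has changed. The point benchmarks raise a related problem. They were set in a document that contains no GSV and now stand beside a GSV analysis, so an observed GSV difference may be judged against 2.7 or 4.5 points that were not derived for it.

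**Working it through.** **1. Match endpoint to analysis.**

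| Item | Adaptive Behavior Composite, standardized | GSV mean |
|---|---|---|
| Described in the protocol | Yes (8.1.5.1) | No |
| Named in SAP Table 1 and 4.2.1 | Composite named, scale not stated | No |
| Named in SAP 4.2 as the primary analysis | No | Yes |
| ANCOVA tables in SAP Appendix 1 | 0 | 9 (ABC, Socialization, Communication, each with no interaction, age interaction and IQ interaction) |
| By-arm change-from-baseline tables | Yes | Yes |

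Read alone, SAP 4.2.1 and Table 8 would apply the ANCOVA to the composite score. SAP 4.2 and the output list resolve that to GSV. The SAP is therefore inconsistent with itself as well as with the protocol.

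**2. Reproduce the plan's figures.** Inputs are from SAP 2.1 and 2.2: 28 evaluable per arm, SD of change 8.0, target 4.5 points, one-sided alpha 0.10 (z = 1.2816).

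- Standard error of a difference: 8.0 × √(2/28) = 2.138.
- Just-significant difference: 1.2816 × 2.138 = 2.74 points (stated 2.7).
- Power at 4.5 points: Φ(4.5/2.138 − 1.2816) = Φ(0.823) = 79.5% (stated as at least 80%).
- Enrolment: 84/0.80 = 105 (stated 105).

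The sample-size arithmetic is not in question.

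**3. Dependence on scale.** The 2.7 points is 0.2673 × 1.2816 × SD, so it is a fixed multiple of the SD. In SD units the just-significant difference is 1.2816 × √(2/28) = 0.34 and the target is 4.5/8.0 = 0.56. Neither depends on the metric. In points they do. The documents give no SD for GSV change, so the range below is assumed:

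| Assumed SD of GSV change | Just-significant difference (points) |
|---|---|
| 4 | 1.37 |
| 6 | 2.06 |
| 8 | 2.74 |
| 10 | 3.43 |
| 12 | 4.11 |

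Only an SD near 8 returns the stated 2.7.

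**4. Check the standard score as the SAP derives it.** SAP 4.1.3 gives V-scale scores of 1 to 24. Table 7 sums three of these per domain, then sums the three domains.

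- Domain: 3 × 1 = 3 to 3 × 24 = 72.
- Composite: 9 × 1 = 9 to 9 × 24 = 216.

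The composite span fits neither the 20 to 140 in SAP 4.1.3 nor the 20 to 160 in Protocol 8.1.5.1. An ANCOVA run on the variable as written would analyse a third metric, not the protocol's score.

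**The case against.** Several points on the other side stand.

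- **The objectives tables do not say standardized.** That scale comes from Protocol 8.1.5.1, while Protocol 9.2 and 9.4.2 refer only to a Vineland-3 composite. The standard-score reading is the natural one, since it is the only scale the protocol describes, but it is an inference.
- **The standard scores are not ignored.** A reader might infer that the arms are not compared on them at all. They are summarised by arm, including change from baseline. What is missing is the model-based comparison.
- **The study is exploratory.** Protocol 9.1 and SAP 2.1 plan no formal hypothesis test. This lowers the stakes but does not remove them, because SAP 2.1 still bases gating on ANCOVA p-values.
- **The detectable difference is framed as standardized.** SAP 2.1 describes it that way, and no decision rule uses raw points. With 4.5 points held fixed and the SD varied over the assumed 4 to 12, power would run from 99.8% to 54.8%. A reader might infer from this that the trial may be badly underpowered. The documents do not support that: they give neither a GSV SD nor a 4.5-point GSV target, and at 0.56 SD power is about 79.5% on any metric.
- **The GSV choice is written down and reproducible.** It precedes the primary analysis, which SAP 1.2 places at database lock. Nothing shows a scale picked after seeing results, or that GSV is a poor measure.

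Parts of the SAP were not available for this check, so a rationale given there cannot be excluded. It would not remove the conflict between SAP 1, 4.2.1 and 4.2.

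**Conclusion.** The point holds as a mismatch between the declared endpoint and the analysed score. All nine Vineland ANCOVA tables use GSV means. The composite on the protocol's standardized scale, and the corresponding Socialization and Communication scores, get descriptive summaries only, while SAP 1 reports no change.

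The point benchmarks are unattached to a scale rather than wrong. They carry over to the GSV mean in points only if its SD of change is about 8; in SD units (0.56 and 0.34) they carry over regardless. No loss of power is shown.

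The conclusion rests on reading the composite as Protocol 8.1.5.1 describes it. It matters because, without a change, the trial can report a descriptive result but no adjusted treatment effect for the protocol's score. The Table 7 derivation adds to the problem, since the standard score as written spans 9 to 216 and cannot stand in for that score.

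**What to change.** Before unblinding; if unblinding has already happened, label the additions post hoc.

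1. In SAP 1, Table 1 and 4.2.1, state that the primary and gating score is the GSV mean and that this changes the protocol endpoint. Make the same statement for the two Vineland secondary endpoints.
2. Reconcile the Table 7 standard-score derivation with the scoring manual the SAP cites and with the two stated ranges (20 to 140 and 20 to 160). Then add the no-interaction ANCOVA on the ABC, Socialization and Communication standard scores as supportive analyses, reported beside the GSV results.
3. In SAP 2.2, state which scale the 4.5, 8.0 and 2.7 points refer to, or give the benchmarks in SD units.

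The cost is SAP wording, a corrected derivation and three extra tables from data already collected. The drawback is two readings of one instrument, which may disagree; naming the gating score in advance settles which one counts.

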4.2.2.1 Subgroup Analyses for Primary and Secondary Efficacy Endpoints

The generalizability of Vineland-3 ABC three-domain GSV composite and RBS-R total score results when comparing any active treatment arm to placebo will be investigated by estimating the treatment effect in subgroups based on geographic region (North America vs. Europe), rater change (yes vs. no), site type (academic vs. ASD research sites), age categories (adolescents vs. adults), and IQ categories (high functioning vs. low functioning).

The dependence of BAI total score and RBS-R total score results on a history of clinical diagnosis of anxiety at baseline (yes vs. no) will be investigated.

For RRB endpoints RBS-R total score, CRRI total score and CGII (RRB domain) subgroups of male vs female will be investigated.

Summaries of these subgroup analyses will be provided in forest plots.

Selected categories used in this section, and their characteristic values are provided in the following table:

Table 9 Selected Categories and Characteristic Values

Category	Characteristic Value
Anxiety at Baseline	Preferred Terms: Anxiety, Anxiety Disorder, Generalized
	Anxiety Disorder, Social Anxiety Disorder
ASD Research Site	Southwest Autism Research And Resource Center, UNITED STATES
	Nathan Kline Institute, UNITED STATES
	APG Center for Autism & ADHD,

UNITED STATES
Okanagan Clinical Trials, CANADA

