4.3 SUPPORTIVE EXPLORATORY EFFICACY ENDPOINTS ANALYSES

Additional exploratory analyses will be performed in a descriptive manner for continuous endpoints Vineland-3, RBS-R, CRRI, CGI, AASP, PRAS-ASD, BAI, SSP-2, PedsQL™, and PROMIS per treatment arm comprising baseline values, (up to) week 12 values and change from baseline to (up to) week 12 values.

For endpoint CGI, analyses will be performed to get the proportion of subjects in each of the rating categories per treatment arm and per time point.

For the assessment of differences between each Alogabat group and placebo regarding the CGI-I overall score at week 12, a mixed-effects MMRM analysis incorporating data up to 12 weeks of treatment will be used to utilize all the data collected over time with consideration of the variance-covariance matrix of the repeated measures. The model will include the CGI-I overall score as the dependent variable. The effects in the model will include independent variables of the fixed, categorical effects of treatment, assessment weeks relative to the first dose of study medication (i.e., time), and treatment-by-time interaction, along with covariates of the baseline value, age at screening and IQ at baseline. Time will be treated as the repeated variable within a subject. An unstructured variance-covariance structure will be applied to model the within-subject errors.

For the primary, secondary, CRRI and CGI-I endpoints, the ANCOVA will be repeated to model change from baseline data y_{ij} of participants i, and treatment $j \in \{\text{placebo}\}\$ (reference), low dose, high dose) incorporating interactions to the model as follows:

$$y_{ij}=\mu+t_j+a_i+IQ_i+t_j*IQ_i+BL_i+\epsilon_{ij}$$

and

$$y_{ij}=\mu+t_j+a_i+IQ_i+t_j*a_i+BL_i+\epsilon_{ij}$$

where μ gives the overall endpoint mean change, followed by the fixed effect t which models the effect of treatment, age a, IQ, the interactions t^*IQ and t^*a respectively, the endpoint baseline value BL, and ε , which gives the overall error term with $N(0, \sigma_{\varepsilon}^2)$.

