t_<>	Efficacy	Correlation between Baseline EEG beta power and clinical efficacy	
t_pql_tot_cfb	Efficacy	PedsQL™ Total Score Change from Baseline	
t_pql_cfs_cfb	Efficacy	PedsQL [™] Cognitive Functioning Score Change from Baseline	
g_cgii	Efficacy	CGI-I Overall Score over Time	
g_cgis	Efficacy	CGI-S Overall Score over Time	
g_forest	Efficacy	Vineland-3 ABC GSV composite	

	•		
		by Geographic Region with 80% CI	
g_forest	Efficacy	Vineland-3 ABC GSV composite by Rater Change with 80% CI	
g_forest	Efficacy	Vineland-3 ABC GSV composite by Site Type with 80% CI	
g_forest	Efficacy	Vineland-3 ABC GSV composite by Age Category with 80% CI	
g_forest	Efficacy	Vineland-3 ABC GSV composite by IQ Category with 80% CI	
g_forest	Efficacy	RBS-R total score by Geographic Region with 80% CI	
g_forest	Efficacy	RBS-R total score by Rater Change with 80% CI	
g_forest	Efficacy	RBS-R total score by Site Type with 80% CI	
g_forest	Efficacy	RBS-R total score by Age Category with 80% CI	
g_forest	Efficacy	RBS-R total score by IQ Category with 80% CI	
g_forest	Efficacy	RBS-R total score by Diagnosis of Anxiety at Baseline with 80% CI	
g_forest	Efficacy	RBS-R total score by Sex with 80% CI	
g_forest	Efficacy	CRRI total score by Sex with 80% CI	
g_forest	Efficacy	CGII (RRB domain) by Sex with 80% CI	
g_forest	Efficacy	BAI total score by Diagnosis of Anxiety at Baseline with 80% CI	

Certificate Of Completion

Envelope Id: 00A25604873540C595AE83AF56584F0E

Subject: Complete with Docusign: BP41316_SAP_V02.pdf

Source Envelope:

Document Pages: 51 Signatures: 1 Certificate Pages: 4 Initials: 0

AutoNav: Enabled

Envelopeld Stamping: Disabled

Time Zone: (UTC+01:00) Amsterdam, Berlin, Bern, Rome, Stockholm, Vienna

Status: Completed

Envelope Originator:

[name]

IP Address:

Record Tracking

Status: Original

6/28/2024 1:54:12 PM

Holder:

Location: DocuSign

Signer Events

Statistician

F. Hoffmann-La Roche

Security Level: Email, Account Authentication

(Required)

Signature

Timestamp

Sent: 6/28/2024 1:54:56 PM Viewed: 6/28/2024 1:55:15 PM Signed: 6/28/2024 1:55:35 PM

Signature Adoption: Pre-selected Style Signature ID:

With Signing Reasons (on each tab):

10EC3CF5-F664-481F-BAE0-AD933DC0A009

Using IP Address:

With Signing Authentication via DocuSign password

I approve this document

Electronic Record and Signature Disclosure:

Accepted: 11/2/2020 2:09:16 PM

ID: 102e05f3-7156-49ba-9ce4-508e079f28ec

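### The SAP's subgroup plots ask whether treatment effects depend on patient factors, but 11 of the 15 have no estimate of that difference, and two endpoints are contrasted with placebo only inside subgroups

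*SAP*

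**What the plan says.** SAP 4.2.2.1 estimates active-versus-placebo effects within two-level subgroups and displays them in forest plots.

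- **Vineland-3 ABC GSV composite and RBS-R total:** region, rater change, site type, age group and IQ group, with the stated aim of assessing generalizability.
- **Anxiety history:** the sentence begins "The dependence of BAI total score and RBS-R total score results on a history of clinical diagnosis of anxiety at baseline (yes vs. no) will".
- **Sex:** "For RRB endpoints RBS-R total score, CRRI total score and CGII (RRB domain) subgroups of male vs female will be investigated".

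SAP Appendix 1 lists 15 forest plots: Vineland-3 ABC 5, RBS-R 7, CRRI 1, CGI-I RRB domain 1, BAI 1. Every title names the interval level, for example "BAI total score by Diagnosis of Anxiety at Baseline with 80% CI".

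For the whole population, SAP 4.2 and 4.2.2 plan ANCOVA contrasts for the primary, secondary, CRRI and CGI-I endpoints, and for CGI-I specify the overall score. BAI falls under SAP 4.3: "Additional exploratory analyses will be performed in a descriptive manner for continuous endpoints Vineland-3, RBS-R, CRRI, CGI, AASP, PRAS-ASD, BAI" and others. Appendix 1 gives BAI one change-from-baseline table and no ANCOVA. The same section repeats the ANCOVA with a treatment-by-IQ and then a treatment-by-age term for the primary, secondary, CRRI and CGI-I endpoints. No interaction model is planned for region, rater change, site type, anxiety or sex.

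**The concern.** Whether an effect generalises across levels, or depends on a factor, is a question about the difference between two treatment effects. The planned plots show each effect separately. A reader must then compare intervals by eye, and two intervals can differ in whether they cover zero simply because one subgroup is smaller.

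Two endpoints have a further gap. BAI total and the CGI-I RRB domain have no planned whole-population contrast, so a subgroup result on either has no overall estimate beside it. At stake is how the trial's subgroup evidence is read when later studies are designed: apparent responders if the drug does nothing, and apparent failure to generalise if it works equally in everyone.

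**Working it through.** **1. Planning inputs (SAP 2.2).** "Evaluable data from 84 ASD participants provides at least 80% power to detect" "a mean difference between baseline and 12-week follow-up of 4.5 points" "between any active treatment arm and the placebo arm with α = 0.10 error control (1-sided"). "It is assumed that the standard deviation of the differences between baseline and 12 weeks follow up is 8.0 points". With 1:1:1 allocation, 84 evaluable is 28 per arm.

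- SE = 8 × √(2/28) = 2.138.
- Power = Φ(4.5/2.138 − 1.2816) = Φ(0.823) = 79.5%, against the stated 80% or more.
- Minimally detectable difference = 1.2816 × 2.138 = 2.74, against the stated 2.7.
- 84/0.8 = 105, as stated.

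The plan's figures reproduce, so its inputs are used below.

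**2. Count of intervals.** 15 plots × 2 levels × 2 doses = 60. This total is derived, not stated; it assumes each dose is shown separately at each level. Pooling the doses would give 30.

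**3. No effect on any endpoint.** An 80% interval excludes zero with probability 0.20, so 60 × 0.20 = 12 are expected to do so, 6 of them in the drug's favour (pooled doses: 30 × 0.20 = 6 in all). Shared patients and correlated scales leave the expectation unchanged but widen the spread. In a simulation with 28 per arm, subgroup prevalences of 25–50% and assumed correlations of 0 to 0.8 among the RRB scales (0 to 0.4 otherwise), the 5th to 95th percentile of the count ran from about 4 to 21–24. BAI and the CGI-I RRB domain have 4 intervals each: 4 × 0.20 = 0.8 expected, and in the same simulation at least one excluded zero in 53–55% of trials.

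**4. Uniform effect (Vineland inputs only).** Take one dose, a true effect of 4.5 in both levels and a 25/75 split, so 7 and 21 per arm. The half-width is h = t × SE, and P(excludes zero in the drug's favour) = Φ((4.5 − h)/SE), treating h as fixed.

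| n per arm | SE | t (df) | h | P |
|---|---|---|---|---|
| 7 | 4.276 | 1.356 (12) | 5.80 | 0.38 |
| 21 | 2.469 | 1.303 (40) | 3.22 | 0.70 |
| 14 | 3.024 | 1.315 (26) | 3.98 | 0.57 |

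The levels contain different patients, so the chance that exactly one excludes zero is:

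- 25/75 split: 0.38 × 0.30 + 0.62 × 0.70 = 0.55.
- Even split: 2 × 0.57 × 0.43 = 0.49.

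Letting the SD be estimated (noncentral t) changes the first figure to 0.54 and leaves the second at 0.49.

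**5. Coverage by an interaction model.** Vineland-3 ABC and RBS-R, each by age and by IQ, make 4 plots. The remaining 11 are Vineland-3 ABC by region, rater change and site type (3); RBS-R by those three plus anxiety and sex (5); and CRRI by sex, CGI-I RRB domain by sex and BAI by anxiety (3).

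**6. Precision of the missing quantity.** The between-level difference at 7 and 21 per arm has SE = 8 × √(2/7 + 2/21) = 4.94, so its 80% half-width is 1.2816 × 4.94 = 6.3 points. For an even split it is 1.2816 × 8 × √(4/14) = 5.5 points.

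**The case against.** The strongest reply is that the study declares itself exploratory, with no formal hypothesis testing (SAP 2.1 and 2.2; Protocol 9.1), and that forest plots are a conventional descriptive display. Much of this stands, and it rules out several stronger readings.

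- **Undisclosed intervals.** A reader might infer that the intervals are unlabelled. They are not: every output title gives the 80% level. Section 4.2.2.1 merely does not repeat the study-level exploratory statement, and its heading names primary and secondary endpoints while the text also takes in BAI, CRRI and CGI-I.
- **A planned significance rule.** A reader might infer that an interval excluding zero will be declared a subgroup finding. The SAP states no such rule. Gating uses ANCOVA p-values (SAP 2.1), and nothing ties it to the forest plots.
- **No assessment of effect modification.** The age and IQ interaction models exist and concern the two modifiers named in the trial's rationale.
- **No comparison at all for BAI or the CGI-I RRB domain.** By-arm summaries are planned for both instruments, as are CGI rating proportions by arm. What is missing is an overall interval-based contrast. Protocol Table 12 may have intended ANCOVA for exploratory endpoints, but it is too broken in the available text to tell.
- **Transfer of the 55% figure.** It rests on Vineland inputs. No SD or target effect is given for BAI or CGI-I, and Protocol Table 9 marks BAI as not applicable for low-functioning participants, so 28 per arm would not carry over. Among the Vineland plots, the caps support a 25/75 split only for IQ and, in the protocol, for age; both have interaction models.

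The exploratory label does not remove the core point. The section asks about generalizability and dependence, and for 11 plots it plans no quantity that answers the question.

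**Conclusion.** The concern holds in limited form. SAP 4.2.2.1 poses interaction questions but plans separate subgroup estimates. Four of the 15 plots are addressed by the age and IQ models, and only in part: age and IQ enter as individual covariates, so those terms need not equal the plotted adolescent-versus-adult or high-versus-low-functioning difference. Eleven plots have no between-level estimate. For BAI total and the CGI-I RRB domain, the only interval-based comparisons with placebo lie inside subgroups.

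The discordance of about 55% (49% for an even split) illustrates why separate intervals cannot establish dependence. It rests on the Vineland inputs and an assumed split, and is not an error rate of any planned rule. Likewise, 12 of 60 is an expectation only if there is no effect on any endpoint and both doses are shown at both levels; it does not forecast 12 false findings. The change is worth making because it answers the section's own question at very little cost. The primary analysis is not affected.

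**What to change.** 1. For each forest plot, report the between-level difference in treatment effect for each dose (the treatment-by-subgroup term of the ANCOVA) with its 80% CI. Base statements on generalizability or dependence on that estimate, read alongside the planned age and IQ interaction models. State in 4.2.2.1 which model produces the subgroup intervals; the SAP does not currently say.
2. Fit the overall ANCOVA for BAI total and for the CGI-I RRB domain, and show the overall treatment estimate in every plot.

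Optionally, label the section as exploratory and unadjusted; this is editorial and the point does not depend on it.

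The cost is a few lines of SAP text, two overall model fits, an interaction term per plot and an extra row type in the display. No new data are needed. The real downside is precision: on the Vineland inputs the 80% half-width for the between-level difference is about 5.5 to 6.3 points, wider than the 4.5-point planning effect, so these estimates will rarely be conclusive.
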